6.2.1.8 Adverse Event Assessments

Beginning with the Screening visit and through the EOS/ET visit, the Investigator and study personnel will Confidential Page 36 of 59

review each subject's clinical evaluation findings and query the subject directly regarding AEs (see Section 7, Safety Data Collection, Recording and Reporting). Subjects must be followed for AEs until the final required protocol visit or until all drug-related toxicities and SAEs have resolved (or are considered chronic/stable), whichever is later.

6.2.2 Laboratory Evaluations

The following laboratory evaluations will be conducted during the study:

6.2.2.1 Serology test for HIV

During the Screening visit (Visit 1), the Investigator or designee will obtain serum test for HIV. Negative test is required to participate in the study.

6.2.2.2 Test for Hepatitis B&C

During the Screening visit (Visit 1), the Investigator or designee will obtain serum test for Hepatitis B&C. Negative test is required to participate in the study.

6.2.2.3 Pregnancy test

A urine pregnancy test will be performed at the Screening, Baseline and EOS/ET visits for females of childbearing potential (refer to Section 4.2 for definitions). The Baseline urine pregnancy test result must be available and must be negative before the subject applies the first application of study drug. An investigator may repeat the pregnancy test anytime during the study if there is any suspicion or possibility that the subject may be pregnant.

6.2.2.4 Test for Syphilis

The test for Syphilis will be performed if required by applicable local regulations. During the Screening visit (Visit 1), the Investigator or designee will obtain serum test for Syphilis. Negative test is required to participate in the study.

6.2.3 Subject Diary Card Review

The subject will be given a kit of study drug, mirror and a Subject Diary Card to capture application details, and acknowledge any changes in skin reactions, other AEs and concomitant medications during the intervening time between the site visits. Subjects will fill out their diary cards during each treatment cycle noting the following:

- Time and date of application
- Any changes in skin reactions, other AEs and concomitant medication

Subjects will return their completed diary cards to the clinical site at each of the post-baseline visits (visits 3-5 and EOS/ET) for review and filing with the subject's source documents. The Investigator will verify that the subject complied with the application requirements. The study staff will sign off on completed diary card. Any missed application notations will be clarified with the subject and documented. Refer to Section 5.8 for additional information regarding the treatment compliance.

Confidential Page 37 of 59

6.3 Study Procedures

6.3.1 Visit 1: Screening (Day -14 up to -1)

Screening visit will occur at up to 14 days prior to the Baseline. During the screening, the following procedures will be performed:

- Informed Consent
- Collection of Subject Demographics and Medical History
- Concomitant and Prohibited Therapies Review
- Assessment of Vital Signs
- Physical Examination
- Serology test for HIV, Hepatitis B and C
- Urine pregnancy test
- Test for Syphilis (if required)
- Confirmation and documentation of the diagnosis of anogenital warts during the visual inspection (histological confirmation will be obtained if there is any doubt of the diagnosis)
- Eligibility Criteria Check
- Adverse Events Assessment
- Schedule next visit to occur within window

6.3.2 Visit 2: Baseline Visit (Day 0)

- Adverse Events Assessment
- Concomitant and Prohibited Therapies Review
- Assessment of Vital Signs
- Physical Examination
- Urine Pregnancy Test
- Visual Inspection of EAWs
- Assessment of Local Application Site Reactions
- Eligibility Criteria Check
- Randomization
- Study Drug Dispensation
- Subject Diary Card Dispensation
- Training on Study Drug Application
- Training on Subject Diary Card completion and contraception methods
- Schedule next visit to occur within window

6.3.3 Visits 3-6 (Day 7 [Week 1], Day 14 [Week 2], Day 21 [Week 3], and Day 28 [Week 4])

The following procedures will be performed:

- Subject Diary Card Return, Review and Dispensation
- Adverse Events Assessment
- Concomitant and Prohibited Therapies Review
- Assessment of Vital Signs

Confidential Page 38 of 59

- Assessment of Local Application Site Reactions
- Visual Inspection of EAWs. In the case there is a total disappearance of all warts within all treated areas at visits 2, 3, 4, or 5, this visit will be considered an End of Study (EOS) visit. In the case where reduction of warts is absent or incomplete, a new treatment cycle will be initiated for a maximum of four cycles in total for the subject.
- Study Drug Return and Accountability
- Study Drug Dispensation

6.3.4 End of Study / Early Termination (EOS/ET) visit

The visit at which "treatment success" has been achieved will be considered EOS visit.

If "treatment success" has not been achieved through the EOS/ET visit (Day 28±5 [Week 4]), then the subject will be considered "treatment failure" and EOS activities will be performed. Similarly, if the Investigator assesses the subject's condition at any time and determines that the subject's condition has worsened to the degree that it is unsafe for the subject to continue in the study, the subject may be discontinued from the study as "treatment failure". ET visit procedures will be performed, and an alternative treatment will be advised at the Investigator's discretion.

Subjects discontinuing from the study sooner than the Day 28 visit will undergo the ET visit as soon as possible.

Following activities will be performed at EOS/ET visit:

- Subject Diary Card Return and Review
- Adverse Events Assessment
- Concomitant and Prohibited Therapies Review
- Assessment of Vital Signs
- Physical Examination
- Assessment of Local Application Site Reactions
- Visual Inspection of EAWs
- Study Drug Return and Accountability
- Urine Pregnancy Test
- For prematurely discontinuing subjects record reason for discontinuation.

6.3.5 Unscheduled Visit

Subjects will be encouraged to report any complications or adverse effects during their participation. Investigator may evaluate the subject at an unscheduled visit, if subject's condition will be considered as worsening. If the investigator assesses the subject's condition and determines that the subject's condition has worsened to the degree that it is unsafe for the subject to continue in the study, the subject may be discontinued from the study as a treatment failure, an Early Termination Visit conducted, and a standard of care treatment may be advised at the investigator's discretion. The following procedures should be performed at the Unscheduled Visit if required.

- Subject Diary Card Return, Review and Dispensation
- Adverse Events assessment

Confidential Page 39 of 59

- Concomitant and Prohibited Therapies review
- Collection of Vital Signs
- Physical examination
- Assessment of Local Application Site Reactions
- Visual Inspection of EAWs

Confidential Page 40 of 59

7 SAFETY DATA COLLECTION, RECORDING AND REPORTING

The Investigator will monitor each subject for clinical evidence of adverse events on a routine basis throughout the study. The Investigator will assess and record any AE in detail including the date of onset, description, severity, time course, duration and outcome, relationship of the adverse event to study drug, an alternate etiology for events not considered "related" or "probably related" to study drug, final diagnosis, if known, and any action(s) taken. For AEs to be considered intermittent, the events must be of similar nature and severity and each intermittent AE will be reported separately. AEs and SAEs, whether in response to a query, observed by site personnel, or reported spontaneously by the subject will be recorded, monitored and followed-up until the resolution (or until the Investigator deems the event to be stable/chronic).

7.1 Definitions

7.1.1 Adverse Event

An AE is defined as any untoward medical occurrence in a patient or clinical investigation subject administered a pharmaceutical product and which does not necessarily have a causal relationship with this treatment. An AE can therefore be any unfavorable and unintended sign (including an abnormal laboratory finding), symptom, or disease temporally associated with the use of a medicinal (investigational) product, whether the event is considered causally related to the use of the investigational product.

Such an event can result from use of the drug as stipulated in the protocol or labeling, as well as from accidental or intentional overdose, drug abuse, or drug withdrawal. Any worsening of a pre-existing condition or illness is considered an AE. Clinically significant abnormalities are to be followed to resolution (i.e. become stable, return to normal, return to Baseline, or become explainable). Laboratory abnormalities and changes in vital signs are considered AEs only if they necessitate therapeutic medical intervention, and/or if the Investigator considers them to be AEs.

7.1.2 Serious Adverse Events

If an AE meets any of the following criteria, it is to be reported to the Biorasi Safety and Pharmacovigilance as a serious adverse event (SAE) using SAE report form within 24 hours of occurrence or notification to the study site:

Death of Subject	An event that results in the death of a subject.
Life-Threatening	An event that, in the opinion of the Investigator, would have resulted in immediate fatality if medical intervention had not been taken. This does not include an event that would have been fatal if it had occurred in a more severe form.
Hospitalization	An event that results in an admission to the hospital for any length of time. This does not include an emergency room visit or admission to an out-patient facility.
Prolongation of Hospitalization	An event that occurs while the study subject is hospitalized and prolongs the subject's hospital stay.
Congenital	An anomaly detected at or after birth or any anomaly that result in fetal loss.

Confidential Page 41 of 59

Anomaly/birth defect	
Persistent or Significant Disability/Incapacity	An event that results in a condition that substantially interferes with the activities of daily living of a study subject. Disability is not intended to include experiences of relatively minor medical significance such as headache, nausea, vomiting, diarrhea, influenza, and accidental trauma (e.g., sprained ankle).
Other Important Medical Event	An important medical event that may not be immediately life-threatening or result in death or hospitalization, but based on medical judgment may jeopardize the subject and may require medical or surgical intervention to prevent any of the outcomes listed above (i.e., death of subject, life- threatening, hospitalization, prolongation of hospitalization, congenital anomaly, or persistent or significant disability/incapacity). Examples of such events include allergic bronchospasm requiring intensive treatment in an emergency room or at home, blood dyscrasias or convulsions that do not result in inpatient hospitalization, or the development of drug dependency or drug abuse.

7.2 Adverse Event Severity

The Investigator will use the following definitions to rate the severity of each AE and SAE:

Mild	The event is transient and easily tolerated by the subject.
Moderate	The event causes the subject discomfort and interrupts the subject's usual activities.
Severe	The event causes considerable interference with the subject's usual activities and may be incapacitating or life-threatening.

7.3 Causality of Adverse Events

The Investigator will use the following definitions to assess the relationship of the AE/SAE to the use of investigational product:

Related	The event occurred within a reasonable time after drug administration or drug concentration and body fluids demonstrated that the study drug was present: the event could not be reasonably explained by known characteristics including concomitant therapies; the adverse event abated after discontinuing the study drug.
Probably Related	The event has a strong temporal relationship to study drug or recurs on re-challenge and another etiology is unlikely or significantly less likely.
Possibly Related	The event has a strong temporal relationship to the study drug and an alternative etiology is equally or less likely compared to the potential relationship to study drug.
Probably Not Related	The event has little or no temporal relationship to the study drug and/or a more likely alternative etiology exists.
Not Related	The event is due to an underlying or concurrent illness or effect of another drug and is not related to the study drug (e.g., has no temporal relationship to study drug or has a much more likely alternative etiology).

If an Investigator's opinion of possibly, probably not, or not related to study drug is given, an alternate etiology must be provided by the Investigator for the AE.

Confidential Page 42 of 59

7.4 Adverse Event Collection Period

Any AE/SAE prior to the Screening visit will be considered past medical history (PMH). The AE reporting period for this study begins with the signature of the Informed Consent Form and, for unresolved AEs, ends 30 days following the last study medication application. Those events that occur during the screening period and up to the day of the first application of the study drug will be considered Non-Treatment Emergent AEs.

Adverse events that occur during the treatment period (starting from the day of the first application of Study Drug and up to the final protocol required visit) will be considered Treatment Emergent AEs (TEAEs).

SAE(s) that are observed or spontaneously reported during the subject's participation in the trial will be captured and monitored until the Investigator deems the event to be chronic or not clinically significant or the subject to be stable.

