10.1.1 Adverse Events

Adverse events will be coded using the most recent version of the Medical Dictionary for Regulatory Activities (MedDRA) and will be summarized based on frequency and severity of AEs for all treated subjects. Data will be summarized using preferred term and system organ classifications. Summary will show number and percentage of subjects who experience each AE.

If a subject experiences multiple events that map to a single preferred term, the greatest severity and strongest Investigator assessment of relation to study drug will be assigned to the preferred term for the appropriate summaries. Should an event have a missing severity or relationship, it will be classified as having the highest severity and/or strongest relationship to study drug.

Summaries of treatment-emergent AEs will include any AEs reported beginning with the first dose of study drug on Day 1. The occurrence of treatment-emergent adverse events will be summarized by treatment group using preferred terms, system organ classifications, and severity. Separate summaries of treatment-emergent serious adverse events, treatment-emergent adverse events related to study drug, and events leading to the discontinuation of study drug will be generated. All adverse events reported will be listed for individual subjects showing both verbatim and preferred terms.

Confidential

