	from Baseline	Absent	xx (xx.x)	xx (xx.x)	xx (xx.x)	xx (xx.x)
		Present	xx (xx.x)	xx (xx.x)	xx (xx.x)	xx (xx.x)
		Mild	xx (xx.x)	xx (xx.x)	xx (xx.x)	xx (xx.x)
		Moderate	xx (xx.x)	xx (xx.x)	xx (xx.x)	xx (xx.x)
		Severe	xx (xx.x)	xx (xx.x)	xx (xx.x)	xx (xx.x)

Table 14.3.7Summary of Site Reaction by Intensity and Visit, Safety Population

Repeat for Site reactions: dryness, burning/stinging, erosion, edema, pain, itching, and bleeding.

Then Repeat for visit 4, 5, 6 and EOS.

n: number of patients affected. Test Product: Podofilox Topical Gel 0.5% Reference: Condylox® Gel 0.5% Placebo: vehicle that matches the test product

Source: <Dataset>

Program Name: <Pgm name>

Listing: 16.3.7 Date: YYYY-MM-DD Time: HH:MM:SS

Protocol: 16-POD-001 Version 2.0, 15-Jan-2018

Confidential

	Overall Summary o	of Adverse Events, Safe	ety Population	
	Test Product (N=xxx) n (%)	Reference (N=xxx) n (%)	Placebo (N=xxx) n (%)	All Subjects (N=xxx) n (%)
Total number of AEs	XX	XX	XX	XX
Total number of SAEs	XX	XX	XX	XX
Total Number of TEAEs	XX	XX	XX	XX
Total Number of TESAEs	XX	XX	XX	XX
Number of Subjects with:				
At Least One TEAE	xx (xx.x)	xx (xx.x)	xx (xx.x)	xx (xx.x)
At Least One Related TEAE	xx (xx.x)	xx (xx.x)	xx (xx.x)	xx (xx.x)
At Least One Severe TEAE	xx (xx.x)	xx (xx.x)	xx (xx.x)	xx (xx.x)
At Least One TEAE Leading to				
Discontinuation	xx (xx.x)	xx (xx.x)	xx (xx.x)	xx (xx.x)
At Least One TEAE Leading to			× ,	
Death	xx (xx.x)	xx (xx.x)	xx (xx.x)	xx (xx.x)
At Least One TESAE	xx (xx.x)	xx (xx.x)	xx (xx.x)	xx (xx.x)
At Least One Related TESAE	xx (xx.x)	xx (xx.x)	xx (xx.x)	xx (xx.x)
At Least One Severe TESAE	xx (xx.x)	xx (xx.x)	xx (xx.x)	xx (xx.x)
At Least One TESAE Leading to		. ,		
Discontinuation	xx (xx.x)	xx (xx.x)	xx (xx.x)	xx (xx.x)

Table 14 3 8

(S)AE: (Serious) Adverse Event reported from signature of the Informed Consent Form to 30 days following the last study drug application. TE(S)AE: Treatment Emerging (Serious) Adverse Event reported during the treatment period (from the day of the first application of the study drug and up to the last visit). Test Product: Podofilox Topical Gel 0.5% Reference: Condylox® Gel 0.5% Placebo: vehicle that matches the test product

Source: <dataset></dataset>	Listings: 16.3.8.1 – 16.3.8.2 – 16.3.8.3	Snapshot Data DD-MMM-YYYY
Program Name: <pgm name=""></pgm>	Date: YYYY-MM-DD Time: HH:MM:SS	Programmer: < Programmer Initials>

Protocol: 16-POD-001 Version 2.0, 15-Jan-2018

Confidential

Table 14.3.8.1.1

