Summary of Treatment Emergent Adverse Events (TEAEs) by System Organ Class and Preferred Term, Safety Population

	Test Product (N=xxx) n (%)	Reference (N=xxx) n (%)	Placebo (N=xxx) n (%)	All Subjects (N=xxx) n (%)
Total Number of AEs	XX	XX	XX	XX
Number of Subjects with at Least One AE	xx (xx.x)	xx (xx.x)	xx (xx.x)	xx (xx.x)
Number of subjects with at least One AE:				
System Organ Class #1	xx (xx.x)	xx (xx.x)	xx (xx.x)	xx (xx.x)
Preferred Term #1	xx (xx.x)	xx (xx.x)	xx (xx.x)	xx (xx.x)
Preferred Term #2	xx (xx.x)	xx (xx.x)	xx (xx.x)	xx (xx.x)
Preferred Term #3	xx (xx.x)	xx (xx.x)	xx (xx.x)	xx (xx.x)
etc.				
System Organ Class #2	xx (xx.x)	xx (xx.x)	xx (xx.x)	xx (xx.x)
Preferred Term #1	xx (xx.x)	xx (xx.x)	xx (xx.x)	xx (xx.x)
Preferred Term #2	xx (xx.x)	xx (xx.x)	xx (xx.x)	xx (xx.x)
Preferred Term #3	xx (xx.x)	xx (xx.x)	xx (xx.x)	xx (xx.x)
etc				

AE: Adverse Event reported from signature of the informed Consent Form to 30 days following the last study drug application.

N (%): Number of subjects and % of subjects, except for first line where it is specified as Number of AEs.

Test Product: Podofilox Topical Gel 0.5%

Reference: Condylox® Gel 0.5%

Placebo: vehicle that matches the test product

Source: <Dataset>

Listing:16.3.8.1

Program Name: <Pgm name>

Date: YYYY-MM-DD Time: HH:MM:SS

Snapshot Data DD-MMM-YYYY

Programmer: < Programmer Initials>

Protocol: 16-POD-001 Version 2.0, 15-Jan-2018

STATISTICAL ANALYSIS PLAN

Confidential

Table 14.3.8.1.2

Summary of Tretment Emergent Adverse Events (TEAEs) by System Organ Class, Preferred Term, and Severity, Safety Population

		Test Product	Reference	Placebo	All Subjects
		(N=xxx)	(N=xxx)	(N=xxx)	(N=xxx)
	Severity	n (%)	n (%)	n (%)	n (%)
Number of Subjects with at Least One TEAE	Mild	xx (xx.x)	xx (xx.x)	xx (xx.x)	xx (xx.x)
	Moderate	xx (xx.x)	xx (xx.x)	xx (xx.x)	xx (xx.x)
	Severe	xx (xx.x)	xx (xx.x)	xx (xx.x)	xx (xx.x)
	Total	xx (xx.x)	xx (xx.x)	xx (xx.x)	xx (xx.x)
Number of Subjects with at Least One TEAE:					
System Organ Class #1	Mild	xx (xx.x)	xx (xx.x)	xx (xx.x)	xx (xx.x)
	Moderate	xx (xx.x)	xx (xx.x)	xx (xx.x)	xx (xx.x)
	Severe	xx (xx.x)	xx (xx.x)	xx (xx.x)	xx (xx.x)
	Total	xx (xx.x)	xx (xx.x)	xx (xx.x)	xx (xx.x)
Preferred Term #1	Mild	xx (xx.x)	xx (xx.x)	xx (xx.x)	xx (xx.x)
	Moderate	xx (xx.x)	xx (xx.x)	xx (xx.x)	xx (xx.x)
	Severe	xx (xx.x)	xx (xx.x)	xx (xx.x)	xx (xx.x)
	Total	xx (xx.x)	xx (xx.x)	xx (xx.x)	xx (xx.x)

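### SAP Table 14.3.8.1.1 is titled as treatment-emergent events but is footnoted and labelled with the all-AE window, and the AE follow-up end points in the protocol do not agree

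*Protocol*

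**What the plan says.** **Collection.** Protocol 7.4 starts AE reporting at consent and, "for unresolved AEs, ends 30 days following the last study medication application". Protocol 6.2.1.8 has subjects asked about AEs "Beginning with the Screening visit and through the EOS/ET visit". The Schedule of Events (Protocol Appendix B) shows no visit or call after Visit 6.

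**Follow-up.** Protocol 6.2.1.8 follows subjects "until the final required protocol visit or until all drug-related toxicities and SAEs have resolved (or are considered chronic/stable), whichever is later". Protocol 7 follows events until they resolve or are judged stable or chronic, with no day limit. Protocol 4.2 requires events in subjects who discontinue for an AE to be followed until satisfactorily resolved, and points to 7.4 for the detail.

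**Treatment-emergent definition.** Protocol 7.4 places screening-period events outside the TEAE class and counts events "starting from the day of the first application of Study Drug and up to the final protocol required visit". SAP 10.1.1, repeating Protocol 8.3.4, gives the start only: "Summaries of treatment-emergent AEs will include any AEs reported beginning with the first dose of study drug on Day 1".

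**Table shells (SAP 12.1.1).** Table 14.3.8 defines two classes. (S)AEs run from consent to 30 days after the last application, with no restriction to unresolved events. Treatment-emergent events are those "reported during the treatment period (from the day of the first application of the study drug and up to the last visit". Tables 14.3.8.1.2 (severity), 14.3.8.1.3 (causality) and 14.3.8.2 (serious) use that same TEAE window. Table 14.3.8.1.1 has a TEAE title, but its rows count AEs and its only definition is "AE: Adverse Event reported from signature of the informed Consent Form to 30 days following the last study drug application".

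**The concern.** The secondary objective compares the frequency and severity of adverse events between arms, and Table 14.3.8.1.1 is where a reader would look for frequency by term. It is the only TEAE table in the set with a different event window. If programmed as footnoted, it would count events that Protocol 7.4 says are not treatment-emergent, and its totals need not match the severity and causality tables that break down the same events.

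A routine cross-check might not catch this. Its first row is a total of AEs, which matches the label of the all-AE row of Table 14.3.8 rather than the TEAE row, so the two could agree while both include non-treatment-emergent events.

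Two related wording problems sit alongside. The (S)AE footnote of Table 14.3.8 implies that new events are collected for 30 days after dosing, which the protocol does not provide for. And the protocol sections give different answers on when follow-up of an open event stops.

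**Working it through.** **1. The plan's own figure.** The only stated duration that bears on this is study participation of up to 50 days (Protocol Synopsis). Inputs from Appendix B: screening from Day -14, Baseline on Day 0, last visit Day 28 with a 5-day window. Calendar days = 14 + 1 + 28 + 5 = 48 (47 elapsed). The stated figure fits the visit schedule.

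**2. The two event windows.** Dosing days are 1-3, 8-10, 15-17 and 22-24 (Protocol 3.1). For a full-course subject who consents on Day -14:

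| | Start | End |
|---|---|---|
| TEAE window (Protocol 7.4; Tables 14.3.8 TEAE rows, 14.3.8.1.2, 14.3.8.1.3, 14.3.8.2) | Day 1 | Day 28, at latest 28 + 5 = Day 33 |
| Table 14.3.8.1.1 footnote | Day -14 | 24 + 30 = Day 54 |

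The footnote adds:
- before dosing, Day -14 to Day 0: 14 + 1 = 15 days;
- after the nominal last visit: 54 - 28 = 26 days (54 - 33 = 21 to 54 - 23 = 31 over the visit window).

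For subjects who clear early:
- last dose Day 3, visit Day 7: 3 + 30 - 7 = 26;
- last dose Day 10, visit Day 14: 10 + 30 - 14 = 26;
- last dose Day 17, visit Day 21: 17 + 30 - 21 = 26.

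Each becomes 25 to 27 with the 1-day visit window. Early terminators have no fixed interval.

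**3. Which extra events could exist.** AEs are queried from Screening, so pre-dose events can be recorded. Local reactions are scored at Baseline, before the first application (Protocol 6.3.2), and Protocol 6.2.1.7 has every application site reaction recorded as an AE. Read literally, a non-zero Day 0 score could enter the table. After EOS/ET nothing is actively asked, so additions there would be spontaneous reports or findings made while following open events.

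**4. Follow-up end points side by side.**

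| Protocol section | Events covered | End of follow-up |
|---|---|---|
| 4.2 | Events in subjects discontinuing for an AE | Satisfactory resolution, citing 7.4 |
| 6.2.1.8 | Drug-related toxicities and SAEs | Later of final visit and resolution or stability |
| 7 | AEs and SAEs | Resolution or stability |
| 7.4 | Unresolved AEs | 30 days after last application |
| 7.4 | SAEs | Chronic, not clinically significant, or subject stable |

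Section 4.2 relies on 7.4 for a rule that 7.4 does not give for non-serious events, and the 30-day end is absent from 6.2.1.8 and 7.

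**The case against.** The best defence is that the intent is clear. The title of Table 14.3.8.1.1, SAP 10.1.1 and Protocol 7.4 all point to treatment-emergent events, so the footnote and row labels look copied from the all-AE definition and a careful programmer would follow the title. That is the likeliest explanation. It does not make the shell right: the footnote is the only definition printed with the table, and SAP 10.1.1 supplies no end date to override it. SAP 7.4 exempts layout and titles from formal revision but not true differences in data handling, and which events are counted is data handling.

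The defence is right on several stronger readings that a reader might infer:

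- *That the protocol claims 30 days of surveillance for new events and leaves most of it unobserved.* The 30 days in Protocol 7.4 applies to unresolved AEs, so it limits follow-up. Asking about AEs through EOS/ET and then following open events is coherent. Only the SAP footnote, by dropping the restriction, suggests otherwise.
- *That the AE tables cannot agree.* The AE and TEAE counts in Table 14.3.8 are defined separately and are meant to differ. Table 14.3.8.1.1 departs from the other TEAE tables only if its footnote is followed and events exist outside the TEAE window.
- *That SAP 10.1.1 sets a competing TEAE window.* It is silent on the end, which is a gap and not a conflict.
- *That the stated participation length is wrong.* It fits the schedule, and following an open event does not lengthen participation.

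Overlap would also limit the effect on the row for subjects with at least one event. In the reference gel's trials burning alone was reported as 37.1 + 25.9 + 11.5 = 74.5% (Protocol 1.2.3, taking the severity columns as exclusive). Many subjects may therefore already have a TEAE. Any discrepancy would show mainly in event totals and individual term rows.

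**Conclusion.** The point holds as a definition error in one table, with two related wording conflicts. Table 14.3.8.1.1 is wrong as written: its footnote and row labels contradict its title, Protocol 7.4 and its companion tables. The excess window is up to 15 days before dosing and, at nominal visits, 26 days after the last visit. The first part matters more in practice because AEs are actively queried then.

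The number of subjects or events affected cannot be stated, because the documents give no rate for events outside the TEAE window. The conclusion assumes literal programming of the footnote. The same definitions apply to all blinded arms, so no between-arm bias is shown. Efficacy analyses, sample size and power are untouched.

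The documents do not support going further and requiring a 30-day TEAE window or a post-study contact. Ending TEAEs at the final visit is a stated and coherent choice. The correction is worth making because it is cheap and otherwise leaves the programmer to decide what counts as treatment-emergent.

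**What to change.** Before database lock:

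1. Replace the footnote and AE row labels of SAP Table 14.3.8.1.1 with the TEAE definition and labels of the companion tables (first application to last visit), and state that end point in SAP 10.1.1.
2. Rewrite the (S)AE window in the Table 14.3.8 footnote to match Protocol 7.4 and actual collection: consent to EOS/ET, with later information only on events still open at that visit.
3. Reconcile the follow-up end points in Protocol 4.2, 6.2.1.8, 7 and 7.4, including the cross-reference from 4.2 to 7.4. Which end point should apply is for the sponsor to settle.

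Items 1 and 2 cost a few lines in the SAP and its shells. Item 3 is a protocol wording clarification. None of them adds a visit, a call or a data item.
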